1.0 Objectives

To assess the therapeutic efficacy and toxicities of proton radiotherapy with escalated/accelerated dose for patients with inoperable centrally/superiorly located stage Ia (T1, N0, M0), any stage Ib (T2, N0M0) and selected stage II (T3N0M0) non-small cell lung cancer (NSCLC).

Primary goals:

1. Improve the 2 year local control rate at the primary site over historical results
2. Reduce acute and chronic toxicity (according to the NCI Common Terminology Criteria for Adverse Events version 3.0 [CTCAE v3.0])

Secondary goals:

1. Improve the disease specific survival rate at 2 years over historical results.
2. Study the potential of pre- and post treatment PET/CT in predicting clinical outcome.
3. Study the role of biomarkers in predicting therapeutic response and toxicities.

2.0 Rationale

1. Uncontrolled local-regional tumor is a major source for continuous seeding to distant organs and causes eventual treatment failure in medical inoperable stage I NSCLC. With conventional photon radiotherapy, the 2 years progression free survival is 30-50% for stage I NSCLC (Kaskowitz et al), which is significantly less compared with surgical resection (70-80%). The eradication of the local-regional tumor is an essential step for cure.
2. Current literature indicates that there is a dose-response relationship for both local tumor control and survival in stage I NSCLC (Dosoretz et al). However, toxicities related to the high dose of photon treatments limit the potential for dose escalation. For a given level of normal tissue toxicity, the Maximum Tolerable Dose (MTD) of proton radiotherapy (RT) is likely higher than that of conventional photon RT because of the physical characteristics of proton RT (e.g., the Bragg peak, finite range and lower entrance dose). Therefore, proton RT may have an advantage over conventional photon RT in achieving local tumor control and improving survival with reduced toxicities.
3. Our preliminary data showed that high levels of FDG avidity in pre-treatment PET scans correlate with poor survival in NSCLC (Komaki et al). Comparison of pre- and post-treatment PET/CT scans may predict both local control and survival in patients with stage I NSCLC treated with proton radiotherapy.
4. The response of NSCLC to radiation is heterogeneous with a subset of tumors being resistant to radiotherapy. Clinical radiation sensitivity likely differs from patient to patient in terms of tumor response and treatment-related toxicities. Novel biomarkers may help us to identify patients with different radiation sensitivities and individualize each patient's treatment in the future.

Data that support dose escalation and potential associated toxicities for stage I NSCLC:

1. Conventional radiation dose schedules of 60-66 Gy resulted in a 5-year cause-specific survival rate of 13-31% in medically inoperable stage I (T1-2N0M0) NSCLC (Kaskowitz et al, Krol et al). However, this level of radiation dose was still associated with a local regional failure rate of >75% at 5 years. The distant failure rate was also noted to be between 30-40%.
2. A dose-response relationship for disease-free survival in stage I NSCLC has been reported. Dosoretz et al showed that actuarial disease-free survival at 2-years was 50%, 33%, 22%, and < 20% with 70 Gy (n=4), 60-69 Gy (n=116), 50-59 Gy (n=26), and < 50 Gy (n=6), respectively. The actuarial risk for local failure at 3 years was 33%, 60% and 58% for > 70 Gy (n=4), 60-69 Gy (n=91) and 50-59 Gy (n= 19), respectively.
3. The preliminary data from the RTOG 9311 (Bradley et al) phase I dose escalation study showed that acute toxicity rates were acceptable for dose up to 90.3 Gy (less than 15% grade ≥ 3 pneumonitis and no esophagitis). However, late toxicities were more pronounced. Late grade ≥ 3 radiation pneumonitis occurred at a rate of 15% for patients with a V20<25% for patients treated to dose levels of 77.4 Gy or above with fraction size of 2.15 Gy. For patients with a V20 of 25-37%, late grade ≥ 3 pneumonitis occurred at the rate of 15% for the doses of 70.9 Gy or above. Late grade ≥ 3 esophagitis occurred in less than 7% of patients. The rate of late esophagitis was not directly correlated with dose, but it may be related to the volume of the esophagus treated.

Data in support of proton therapy in early stage NSCLC:

1. Shioyama reported the clinical outcome of 28 patients with stage I NSCLC treated with proton radiotherapy to the median fraction of 3 Cobalt Gray Equivalent (CGE) (range 2-6 CGE) and to a median total dose of 76 CGE (range 49-93 CGE). The 5-year overall survival rate was 70% with local control of 89% for stage IA. However, for stage IB, the local control was 39% and the 5-year overall survival was 15%. Only one case of grade 3 acute toxicity and little late toxicity was observed. In this study, the clinical outcome for stage IA patients was comparable to surgical resection. However, for stage IB patients, the result was much worse than surgical resection and 21% patients recurred in the mediastinum. Since PET scanning was not used for clinical staging, it is possible that the group of patients with stage IB was understaged and significant tumor volume was missed.
2. Bush reported his experience in 27 patients with stage I NSCLC treated with proton and photon radiotherapy. The total dose was 73.8 Gy with 45 Gy delivered with photons (1.8 Gy/fraction) and 28.8 CGE delivered with protons (1.8 CGE/fraction). Proton treatments and the last 16 fractions of photon treatments were given as BID. The local control was 87% and the 2-year disease free survival was 86%. Only two patients developed pneumonitis which resolved after oral steroid treatment.
3. Japan National Cancer Center Hospital East reported their result of 36 patients with stage I NSCLC treated with proton radiotherapy to a total dose of 70-94 CGE delivered in 20 fractions. The 2-year local control was 92.6% and the overall survival was 81%. No grade 2 or above acute toxicities were observed. Late grade 3 toxicities were observed in 3 patients. Among 19 patients with stage IB disease, two had local progression and eight developed regional lymph node and/or distant metastasis. Again, understaging without PET could be a concern here.

4. MD Anderson Cancer Center analyzed our preliminary data of phase I/II study in early stage NSCLC treated with dose escalated/accelerated proton therapy (IASLC 2009 presentation). Fifteen patients with medical inoperable T1N0M0 (central location) or T2-3N0M0 (any location) NSCLC were treated on our phase I/II study using dose-escalated proton therapy to 87.5 cobalt-Gray equivalents (CGE) at 2.5 CGE/fraction without adjuvant chemotherapy. At a median follow-up time of 16.5 months (range, 5-24.1 months), no patient had experienced grade 4 or 5 toxicity. The most common adverse effect was dermatitis (grade 2, 11 patients [73%], grade 3, 2 patients [13%]), followed by grade 2 fatigue (5 patients [33%]), grade 2 pneumonitis (1 patient [7%]), grade 2 esophagitis (1 patient), and grade 2 chest wall pain (1 patient). Rates of local control were 93% (14/15), regional lymph node failure 7% (1/15), and distant metastasis 20% (3/15). Twelve patients (80%) were still alive at last follow-up; 2 had died of metastatic disease and 1 of preexisting cardiac disease. In conclusion, proton therapy escalated to ablative doses is well tolerated and produces promising local control rates for medically inoperable early-stage NSCLC. Distant metastasis remains the most common pattern of failure. Longer follow up is needed.

In summary, the standard radiotherapy dose for early stage NSCLC is about 66 Gy with 2 Gy/fraction. However, more than 50% of cancers recur locally. Based on RTOG 9311, which used photon radiotherapy, 90.3 Gy at 2.15 Gy/fraction in patients with lung V20 <25% (mostly early stage lung cancer) was not considered acceptable due to toxicity: Fifteen percent of the patients experienced grade ≥ 3 pneumonitis and there was one case of grade 5 esophagitis. Preliminary data from proton therapy revealed a much lower toxicity profile and promising local control comparable to surgical resection in stage IA patients. However, the reported total doses and fraction sizes of proton radiotherapy varied significantly. The doses used ranged from 70 Gy to 94 Gy and the fraction sizes ranged from 2 Gy to 6 Gy. In many centers, the dose and fraction size were chosen based on the access to the proton facility. Although hypofractionated radiotherapy showed promising results in the literature mentioned above, more clinical studies with long term follow up are needed since hypofractionated radiotherapy is considered to have possible higher long term toxicities, particularly for centrally located lesions.

Our virtual clinical trial (Chang et al. 2006) showed that even dose escalation to 87.5 CGE using proton in stage I lung cancer reduced normal tissue doses compared with photon therapy using the standard dose 66 Gy. In this proposed study, we will use proton radiotherapy to treat inoperable centrally/superiorly located stage Ia (T1, N0, M0), any stage Ib (T2, N0M0) and selected stage II (T3N0M0) NSCLC to a total dose of 87.5 CGE at 2.5 CGE/fraction, which is equivalent to a schedule of 90.3 Gy given in 42 fractions with 2.15 Gy each (for a tumor α/β of 10 Gy), corresponding to a BED_{10} of 109.4 Gy. While 90.3 Gy in 42 fractions was the highest dose considered for the RTOG 9311 dose escalation photon therapy trial, 83.8 Gy in 39 fractions was considered acceptable dose and 90.3 Gy in 42 fractions was considered to be too toxic (Bradley et al. 2005). However, we anticipate that the proposed proton regimen will achieve improved local control with decreased long-term toxicities compared with the highest safe photon dose regimen of RTOG 9311. This expectation is based on significantly higher BED, a potentially reduced impact of accelerated tumor cell repopulation due to the reduced overall treatment time, and reduced dose to critical normal tissue structures due to the superior dose distribution of protons. In addition, preliminary results from the M.D. Anderson phase I/II study show excellent local control and acceptable toxicity with 87.5 Gy. Treatment planning will be based on PET/CT and 4D CT. Local control at the primary site, disease-specific survival, and toxicities will be analyzed and compared with the historical data of photon radiotherapy.

3.0 Patient Eligibility

3.1 Inclusion Criteria:

- 3.1.1. Histologically or cytologically documented NSCLC.
- 3.1.2. Patients with inoperable centrally/superiorly located tumors, defined as those (with any tumor edge measured within 30 days by the CT image using lung window level including simulation CT or MRI or PET/CT) located within 2 cm of the bronchial tree (carina, right and left main bronchi, right and left upper lobe bronchi, bronchus intermedius, right middle lobe bronchus, lingular bronchus, right and left lower lobe bronchi), major vessels (aorta, pulmonary artery trunk, left/right pulmonary artery/vein main branches, superior/inferior vena cava, brachiocephalic artery trunk or left/right brachiocephalic vein, left/right subclavian artery/vein), esophagus, heart, tracheal, pericardium, mediastinal pleural and brachial plexus and vertebral body, but no direct invasion, T1N0M0 (stage IA), or any location of T2N0M0 (stage IB) and T3N0M0 (selected stage II with chest wall involvement) NSCLC.
- 3.1.3. Performance score KPS 60-100.
- 3.1.4. Negative pregnancy test for women of child bearing potential.

3.2 Exclusion criteria:

- 3.2.1. Prior radiotherapy to the chest.
- 3.2.2. Previous or concomitant malignancy other than (a) curatively treated carcinoma in situ of cervix, (b) basal cell carcinoma of the skin, (c) curatively treated superficial transitional cell carcinoma of the urinary bladder, and (d) early stage tumor treated more than 2 years for cure with life expectancy more than 5 years .
- 3.2.3. Pregnancy. (Patients, both men and women, of child bearing potential should use an effective method of birth control throughout their participation in this study.)

4.0 Pre-treatment evaluation

- 4.1 Complete History and Physical: A complete history and physical to include performance status, recent weight loss, and concurrent non-malignant disease and its therapy will be recorded within 30 days before registered. (Table 1)
- 4.2 Laboratory and Radiographic Tests
 - 4.2.1 Laboratory studies will include a CBC with differential, platelet count, electrolytes, BUN, creatinine within 30 days. LFTs will be optional. 10 ml of additional peripheral blood will be collected optionally at the time of pre-registration blood work up. The blood sample will be frozen using -80 degree centigrade refrigerator for future biomarker studies. In the future, a separate protocol will be developed for the biomarker studies. (Table 1)
 - 4.2.2 Chest X-ray, MRI or CT scans of the brain, CT of chest or PET scan should be done within 3 months prior to radiotherapy. PET/CT scan is preferred whenever possible. Radionuclide bone scan is optional.
 - 4.2.3 PFTs including FEV1, DLCO, TVC, FEV should be obtained within 3 months prior to radiotherapy. EKG is required within 3 months as a baseline test. Cardiac SPECT is recommended if lesion is close to heart and cardiac toxicity

is of concern and/or when EKG is abnormal.

5.0 Evaluation Criteria

5.1 Treatment evaluation:

Acute radiation reactions including esophagitis, pneumonitis and other adverse events will be evaluated weekly during the course of treatment. The adverse events will be graded according to the National Cancer Institute (NCI) Common Terminology Criteria for Adverse Events, version 3.0 (CTCAE 3.0). Laboratory studies will include a CBC with differential, platelet count every three weeks during the radiotherapy.

5.2 Post-treatment evaluation:

Patient follow-up is recommended 6 weeks after RT and then required every 3 months (± 1 month) for two years, then every 6 months (± 1 month) for three years and then annually for the rest of the patient's life, which is the standard of care. For the purpose of this protocol, we are going to follow the patients for a minimum of two years. Afterwards, patients will be continuously followed according to the standard of care. Follow-up will be conducted at the treating institution or other clinical facilities. If the follow-up is performed at other facilities, the information about medical history, physical examination, PFT, image data and radiologist's report must to be sent to the treating institution to be reviewed and documented. Follow-up at the treating institution is strongly recommended.

Two Pulmonary function tests will be performed within first one year ± 5 month after the completion of RT, then annually for two years. It is preferred that PFT is performed in the second and fourth follow up visit after completion of concurrent radiotherapy and chemotherapy, and then annually for two years. If no 6 week follow-up, then PFT is preferred to be performed in the first and third visit. EKG will be conducted in the third or fourth f/u visit and then annually for two years. If cardiac toxicity is of concern based on treatment plan and/or when EKG is abnormal, cardiac SPECT should be performed in the third or fourth f/u visit and then as clinically indicated. Physical examination, medical history, and CXR will be performed in every follow up. A chest CT scan will be performed in the second follow up after radiotherapy and then every three months (± 1 month) for two years and then every 6 months (± 1 month) for 3 years; then annually. PET scan is required between 2-6 months after finishing treatment, including chemotherapy, When a PET scan is available for the follow up visit, a chest CT is not required for this visit. A PET/CT scan is preferred whenever possible.

All diagnostic exams and follow up are subjected to insurance approval or patients' affordability or patients' compliance. If there are metastatic tumors or tumor recurrences, all follow-ups and exams are still recommended.

Local control at the primary site will be evaluated by a series of CT scans of the chest with contrast (if possible) as stated above. If an abnormal lesion is suspicious for recurrent disease by CT image, PET or PET/CT scan is required to evaluate for recurrence and biopsy is recommended to confirm the recurrence. For un-confirmed recurrent disease, continuing follow up images including CT or PET should be considered. Timing of recurrence will be scored at the time of first image (PET and/or CT) showing

abnormalities. Two-year progression free survival (PFS) rate will be calculated. PET information will be considered for calculation of PFS particularly for distant metastasis and/or additional lesions.

Progression free survival will be evaluated.

Grade \geq 3 acute and chronic toxicities by Common Terminology Criteria for Adverse Events, version 3.0 (CTCAE 3.0) will be analyzed.

Response assessment: This protocol will use a modified version of the international criteria proposed by the Response Evaluation Criteria in Solid Tumors (RECIST) Committee [JNCI 92(3): 205-216, 2000] See <http://ctep.info.nih.gov/guidelines/recist.html> for further details. Additional definitions beyond the RECIST guidelines specific to this protocol are incorporated to define local control as described below.

Response Criteria

Evaluation of Target Lesions

Complete Response (CR): Disappearance of the target lesion; ideally, this determination will be made based on CT image evaluation. Negative PET can be also considered to be a CR.

Partial Response (PR): At least a 30% decrease in the LD (The longest diameter for the target lesion will be calculated from the treatment planning CT scan using pulmonary windowing and reported as the baseline LD) of the target lesion, taking as reference the baseline LD; ideally, this determination will be made based on CT image evaluation.

Stable Disease (SD) Neither sufficient shrinkage to qualify for CR/PR above nor sufficient increase to qualify for LE below, taking as reference the smallest LD since the treatment started.

Local Enlargement (LE): At least a 20% increase in the LD of target lesion, taking as reference the smallest LD recorded since the treatment started; ideally, this determination will be made based on CT image evaluation.

Local Progression (LP): Refers to the primary treated tumor after protocol therapy and corresponds to meeting both of the following two criteria: 1) Increase in tumor dimension of 20% as defined above for local enlargement (LE); 2) The measurable tumor with criteria meeting LE should be avid on PET imaging with uptake of a similar intensity as the pretreatment staging PET, OR the measurable tumor should be biopsied confirming viable carcinoma.

For outcome analysis, Marginal Failures (MF; see below) will also be counted as LP; however, they should be distinguished specifically as MF, not LP,. The EORTC criteria for post-treatment PET evaluation will be used as a basis for evaluation in cases more difficult to assign as to whether the uptake is pathologic for cancer recurrence vs. inflammation.⁴⁶

Local Control (LC) The absence of Local Progression.

Evaluation of Non-Target Lesions:

Marginal Failure (MF): Refers to the appearance after protocol therapy of a measurable tumor appearing since treatment within 1.0 cm of the treated PTV and meeting the following two criteria: 1) Enlarging tumor dimensions corresponding to a 20% increase in the longest diameter compared to initial appearance on imaging evaluation. Ideally, this determination will be made based on CT image evaluation; 2) The measurable tumor within 1.0 cm of the treated PTV should be avid on PET imaging with uptake of a similar intensity

as the pre-treatment staging PET, OR the measurable tumor should be biopsied confirming viable carcinoma.

Regional Failure (RF): Refers to the appearance after protocol therapy of measurable tumor within lymph nodes along the natural lymphatic drainage typical for the location of the treated primary disease only with dimension of at least 1.0 cm on imaging studies (preferably CT scans) within the lung, bronchial hilum, or the mediastinum. Equivocally appearing enlarged lymph nodes should be positive on PET imaging or biopsied to confirm involvement with carcinoma.

Metastatic Dissemination (MD): Refers to the appearance after protocol therapy of cancer deposits characteristic of metastatic dissemination from NSCLC. Appropriate evaluations for making this determination include physical examination and imaging studies. PET scan OR biopsy to confirm MD is encouraged but not required.

PFS at the primary site: Patient remains alive without **local** progression (**LP**) at the primary site.

Criteria for going off proton treatment:

1. Development of distant metastasis during the proton radiotherapy.
2. Development of unpredictable, irreversible, or persistent non-hematological grade 4 toxicity.
3. Patient refusal or non-compliance of treatment requirements.

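### A biopsy-proven recurrence at the field margin is not a local failure until it has also grown 20% from its own first appearance; a narrower gap of the same kind exists for the primary tumour

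*Combined protocol and SAP*

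**What the plan says.** All of this is in section 5.2 (Post-treatment evaluation and the Response Criteria that follow) unless noted.

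- **Marginal failure (MF).** The lesion must be a "measurable tumor appearing since treatment within 1.0 cm of the treated PTV and meeting the following two criteria". The first criterion is "Enlarging tumor dimensions corresponding to a 20% increase in the longest diameter compared to initial appearance on imaging evaluation". The second is PET uptake similar to the staging scan, "OR the measurable tumor should be biopsied confirming viable carcinoma".
- **Local progression (LP).** This "corresponds to meeting both of the following two criteria": local enlargement, and the same PET-or-biopsy test. Enlargement means "At least a 20% increase in the LD of target lesion, taking as reference the smallest LD recorded since the treatment started".
- **Scoring.** MF is pooled with LP for the outcome analysis, and local control is simply the absence of LP.
- **Work-up.** When CT is suspicious, "PET or PET/CT scan is required to evaluate for recurrence and biopsy is recommended to confirm the recurrence". The recurrence is dated to the first abnormal image.
- **Imaging.** "A chest CT scan will be performed in the second follow up after radiotherapy and then every three months", with a one-month window either way, for two years, and then every 6 months.
- **Analysis (section 9.0).** Two-year local control is tested at 50% against 75% in 40 patients, one-sided 5%, and estimated by Kaplan-Meier. No censoring rule is given for salvage treatment or death.

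**The concern.** In both definitions the biopsy clause sits inside the second criterion, as the alternative to PET. Histological proof therefore does not make a lesion a failure on its own.

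For MF this matters every time. The reference for growth is the lesion's own first appearance, so at least one later measurement is needed, while the work-up rule recommends biopsy as soon as CT is suspicious. If the biopsy is positive and the lesion is then treated, or is not measured again, the growth test may never be met. The least disputable kind of local failure then drops out of the primary endpoint. For such cases the error has one direction, towards local control. Regional failure and metastatic dissemination carry no growth test, so the gap lies only in the two definitions that feed the primary endpoint.

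**Working it through.** **1. The definitions as logic.**

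- MF = new lesion within 1.0 cm of the PTV AND 20% growth from first appearance AND (PET avid OR biopsy positive).
- LP = 20% growth from the smallest diameter AND (PET avid OR biopsy positive).
- Local control = NOT (LP or MF).

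| Situation | Growth test | Biopsy | Result under 5.2 |
|---|---|---|---|
| New marginal lesion, first detection | cannot be met | positive | not MF |
| Same lesion, later 20% larger | met | positive | MF, dated to first abnormal image |
| Same lesion, treated or not re-measured before 20% growth | never met | positive | never an event |
| Primary, at least 20% above smallest diameter when biopsied | met | positive | LP |
| Primary, less than 20% growth and never reaching it | not met | positive | never an event |

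Rows 3 and 5 are the gap. Row 4 shows why it is narrower for LP: the growth that raises suspicion may already satisfy the test.

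**2. The plan's own power figure.** Inputs from section 9.0: n = 40, 50% against 75%, one-sided 5%, stated power 93%.

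- Normal approximation with null variance: z = 0.25 × √40 / 0.5 − 1.645 = 3.162 − 1.645 = 1.517, power 93.5%.
- Exact binomial: the smallest count with size at most 5% is 26. P(X ≥ 26 | 40, 0.50) = 0.040 and P(X ≥ 26 | 40, 0.75) = 0.946.

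The stated 93% is reproduced closely. The 26/40 boundary is derived here; the plan names no cut-off.

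**3. Effect of one case.**

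- Scored as controlled: 1/40 = 2.5 percentage points.
- Censored instead: take 10 true failures in 40 (75% control), everyone else followed for 2 years, and one failure censored. If it is censored before all other events, Kaplan-Meier gives 30/39 = 76.9%. If after all of them, it gives 31/40 = 77.5%. Censoring does not restore the failure.

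**4. When the test result would change.** Exact one-sided p against 50%: 26/40, 0.040; 25/40, 0.077; 24/40, 0.134. An observed 26/40 that contains one or two such cases would not be significant if they were counted.

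**5. Range over an assumed share.** Let m be the share of true local failures missed this way. The documents give no value. Apparent control = 1 − (1 − p)(1 − m).

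| m | Apparent control, true 50% | P(≥26), true 50% | P(≥26), true 75% |
|---|---|---|---|
| 0 | 50% | 4.0% | 94.6% |
| 5% | 52.5% | 7.6% | 96.4% |
| 10% | 55% | 13.3% | 97.7% |
| 20% | 60% | 31.7% | 99.2% |

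The lower rows show sensitivity to m; they are not a forecast.

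**The case against.** Several points limit the reach of this.

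- **LP and MF are not equally affected.** A reader might infer that they are. LP growth is taken from the smallest diameter and may already be present when biopsy is prompted. This stands.
- **Not every proven and treated recurrence is scored as controlled.** A lesion that later grows 20% becomes an event, dated back to the first abnormal image. A patient who dies or has salvage may well be censored in a Kaplan-Meier analysis. In addition, progression-free survival at the primary site, defined in the same section, requires the patient to be alive. This stands as to labelling. However, section 9.0 tests local control, and censoring also omits the failure.
- **A second measurement need not wait for the next routine CT.** PET is required for a suspicious CT, the section 6.0 schema lists imaging at relapse, and follow-up is still recommended after recurrence. This stands in part: 20% growth may not show over a short interval, all exams depend on insurance, affordability and compliance, and the instruction to consider continued imaging is directed at unconfirmed lesions.
- **The work-up text does not contradict the definitions.** One might infer a direct conflict, since biopsy is said to confirm recurrence. But that text sets work-up and dating and leaves local control to the definitions below it. For the same reason it cannot repair them.
- **The frequency is unknown and probably small.** A case needs a biopsy that is only recommended, too little growth, and no later growth. The sponsor's preliminary series in section 2.0 had 1 local failure in 15, which scales to 40 × 1/15 = 2.7 in 40 (median follow-up 16.5 months). This stands.
- **Inflation relative to the 50% historical rate is not established.** The documents do not say how the historical series defined local failure. This stands.

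**Conclusion.** The wording point holds. A biopsy-proven marginal recurrence without documented 20% growth from first appearance is not an event in the primary endpoint, and the same is true in a narrower set of cases at the primary site. For these patients the bias is towards local control, whether they are scored as controlled or censored.

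The size is modest and rests on assumption: about 2.5 points per case in a simple 40-patient proportion, with an unknown and probably low number of cases. The documents do not support the inference that the trial's conclusion is likely to be overturned. That would need a result near 26/40 (65%), a boundary the plan does not state and well below the anticipated 75% (30/40). Confidence is high for the reading of the definitions and low for their practical effect. It is worth correcting because the correction is cheap.

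**What to change.** Add one sentence to the LP and MF definitions in section 5.2: where a lesion is suspicious on imaging and biopsy confirms viable carcinoma, at the primary site or within 1.0 cm of the treated PTV, it counts as LP (or MF) whatever the change in longest diameter, dated to the first abnormal image under the existing dating rule. Keep growth plus PET as the test for lesions without a positive biopsy. Since the event is then dated to that first image, later salvage or death no longer decides how a proven case is scored.

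No extra scan, biopsy or patient is needed, and the sample size and nominal power do not change. There are two costs. The reported local control rate may be slightly lower. The endpoint will also depend somewhat more on who is biopsied, because biopsy is only recommended and two institutions take part. Reporting a sensitivity analysis under the current two-part definition would show how much this matters.
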